7.2 Discontinuation from the Study

Participants who request to discontinue study treatment will remain in the study and must continue to be followed for protocol-specified follow-up procedures. The only exception to this is when a participant specifically withdraws consent for any further contact with him/her or persons previously authorized by participant to provide this information.

- Participants should notify the investigator of the decision to withdraw consent from future follow-up **in writing**, whenever possible.
- The withdrawal of consent should be explained in detail in the medical records by the investigator and entered on the appropriate CRF page.

- In the event that vital status (whether the participant is alive or dead) is being measured, publicly available information should be used to determine vital status only as appropriately directed in accordance with local law.
- If the participant withdraws consent for disclosure of future information, the Sponsor may retain and continue to use any data collected before such a withdrawal of consent.

7.3 Lost to Follow-Up

- All reasonable efforts must be made to locate participants to determine and report their ongoing status. This includes follow-up with persons authorized by the participant.
- Lost to follow-up is defined by the inability to reach the participant after a minimum of 3 documented phone calls, faxes, or emails as well as lack of response by participant to one registered mail letter. All attempts should be documented in the participant's medical records.
- If it is determined that the participant has died, the site will use permissible local methods to obtain date and cause of death.
- If investigator's use of third-party representative to assist in the follow-up portion of the study has been included in the participant's informed consent, then the investigator may use a Sponsor retained third-party representative to assist site staff with obtaining participant's contact information or other public vital status data necessary to complete the follow-up portion of the study.
- The site staff and representative will consult publicly available sources, such as public health registries and databases, in order to obtain updated contact information.
- If after all attempts, the participant remains lost to follow-up, then the last known alive date as determined by the investigator should be reported and documented in the participant's medical records.

8 STUDY ASSESSMENTS AND PROCEDURES

- Study procedures and timing are summarized in the Schedule of Activities (Section 1.3).
- Protocol waivers or exemptions are not allowed.
- All immediate safety concerns must be discussed with the Medical Monitor immediately upon occurrence or awareness to determine if the participant should continue or discontinue treatment.
- Adherence to the study design requirements, including those specified in the Schedule of Activities (Section 1.3), is essential and required for study conduct.
- All screening evaluations must be completed and reviewed to confirm that potential participants meet all eligibility criteria before randomization. The investigator will maintain a screening log to record details of all participants screened and to confirm eligibility or record reasons for screening failure, as applicable.
- Procedures conducted as part of the participant's routine clinical management (eg, blood count) and obtained before signing of informed consent may be utilized for screening or baseline purposes provided the procedure meets the protocol-defined criteria and has been performed within the timeframe defined in the Schedule of Activities (Section 1.3).

8.1 Efficacy Assessments

8.1.1 Urinary Output

4-Hour urinary output after the 40 mg furosemide bolus will be measured at the time points indicated in the Schedule of Activities (Section 1.3) and [Table 8](#). The 4-hour urinary output after the 40 mg furosemide bolus in the BMS-986231 treatment period will be compared to baseline (4-hour urinary output after 40 mg furosemide bolus in placebo period).

8.1.2 Fractional Excretion of Na (FeNa) and K (FeK)

The plasma and urine concentrations of Na and K will be measured at the time points in the Schedule of Activities (Section 1.3), in [Table 7](#) (blood sampling time points) and in [Table 8](#) (urine collection intervals). The FeNa (%), FeK (%) and the concentration ratio of urinary sodium to urinary furosemide after the 40 mg furosemide bolus (collected 4-8 hours post-start infusion) will be compared to baseline (4-8 hour levels post-start infusion placebo period).

8.1.3 Imaging Assessment for the Study

Echocardiography

Assessments will be done at the time points indicated in the Schedule of Activities (Section 1.3).

Echocardiography to assess congestion: A targeted echo protocol will be implemented with assessment of the diameter of inferior vena cava (IVC), LV systolic and diastolic volumes, Ejection Fraction (Simpson), ratio between early mitral inflow velocity and mitral annular early diastolic velocity (E/e'), left atrial (LA) volumes (min and max), visual assessment of mitral regurgitation (MR) and tricuspid regurgitation (TR), tricuspid annular plane systolic excursion (TAPSE)/pulmonary artery systolic pressure (PASP) and jugular venous diameter.

Any incidental findings of potential clinical relevance that are not directly associated with the objectives of the protocol should be evaluated and handled by the investigator as per standard medical/clinical judgment.

Lung Ultrasound

Lung ultrasonography (LUS) has emerged as a noninvasive, semi-quantitative diagnostic tool for the assessment of extravascular lung water in HF. B-lines on LUS are vertical, hyperechogenic artifacts which arise from the pleural line and can be quantified. B-lines count showed higher sensitivity than the clinical examination or chest radiography in the identification of pulmonary edema. B-lines counts (28 zones) will be done at the time points indicated in the Schedule of Activities (see Section 1.3) prior to start of study drug infusion, just before furosemide bolus and end of infusion.

Whole Body Bio-impedance

Noninvasive cardiac system (NiCaS) device will non-invasively assess CO, stroke volume index, total body water, total peripheral resistance based on whole body bio-impedance; it has been

demonstrated to meet Food and Drug Administration (FDA) standards for bioequivalence when compared to thermodilution-based CO methods.³¹

8.2 Adverse Events

The definitions of an AE or SAE can be found in [APPENDIX 3](#).

AEs will be reported by the participant (or, when appropriate, by a caregiver, surrogate, or the participant's legally authorized representative).

The investigator and any designees are responsible for detecting, documenting, and reporting events that meet the definition of an AE or SAE and remain responsible for following up AEs that are serious, considered related to the study treatment or the study, or that caused the participant to discontinue before completing the study.

Contacts for SAE reporting specified in [APPENDIX 3](#).

8.2.1 ***Time Period and Frequency for Collecting AE and SAE Information***

The Reference Safety Information in Sections 5.6.1 and 5.6.2 of the IB¹⁶ should be used to determine the expectedness of SAEs for expedited reporting.

The collection of nonserious AE information should begin at initiation of study treatment until 24 hours after end of infusion in each treatment period of dosing (Schedule of Activities in Section 1.3). Nonserious AE information should also be collected from the start of a placebo lead-in period or other observational period intended to establish a baseline status for the participants.

All SAEs must be collected from the time of signing the consent, including those thought to be associated with protocol-specified procedures and within 30 days of discontinuation of dosing.

- After these time periods, the investigator must report any SAE that occurs after these time periods and that is believed to be related to study drug or protocol-specified procedure (eg, a follow-up skin biopsy).
- Medical occurrences that begin before the start of study treatment but after obtaining informed consent will be recorded on the appropriate section of the paper Safety Report Form.
- All SAEs will be recorded and reported to Sponsor or designee within 24 hours, as indicated in [APPENDIX 3](#).
- The investigator will submit any updated SAE data to PRA Drug Safety within 24 hours of updated information being available.

Investigators are not obligated to actively seek AEs or SAEs in former study participants. However, if the investigator learns of any SAE, including a death, at any time after a participant has been discharged from the study, and he/she considers the event reasonably related to the study treatment or study participation, the investigator must promptly notify the Sponsor.

The method of evaluating, and assessing causality of AEs and SAEs and the procedures for completing and reporting/transmitting SAE reports are provided in [APPENDIX 3](#).

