ECG	X	ECGs should be recorded after the participant has been supine for at least 5 minutes. At screening, single ECGs will be recorded.
Laboratory Tests	X	Includes blood (hematology, serum chemistry, NT-proBNP or BNP [details in the protocol section]) and urine samples. Participants are required to fast for at least 10 hours prior to the collection of specimens for clinical laboratory tests (details in the protocol Section 8.4.6).
Pregnancy Test	X	For WOCBP only.

Table 2: On Treatment Procedural Outline (CV013-034)

Table 2: On Treatment Procedural Outline (CV013-034)

Procedure	Treatment Period			Notes
	Period 1 Day 1	Washout (7-28 days)	Period 2 Day 1	
		Washout between periods should be at least 7 days and no more than 4 weeks.		
Follow-up call/assessment	X		X	
To be done at Day 2 of each period. Will inquire about general status and occurrence of any AEs.
 
For each period, subjects must remain for at least 3.5 hours after the end of infusion^a. Patients may stay overnight or may be discharged the same day 3.5 hours after end of infusion^a if certain conditions are met (see Section 4.1 for details)

Laboratory Tests				
Hematology and Serum Chemistry	X		X	Laboratory tests will be performed in the morning of each treatment day (H0 [before start of infusion], H4 [just before furosemide bolus], and H8). See protocol Section 8.4.6 for details.
Pregnancy Test (WOCBP only)	X		X	
Blood sampling for PK (furosemide and BMS-986231 [and its metabolites])	X		X	
Blood sampling for PK will be done at H0 (before start of infusion), H2 and at H4 hours (just before furosemide bolus), H5, H6, H8 (or end of infusion^a) and H10 (2 hours after the end of the infusion^a) in each treatment period.
 
In addition, PK samples should be taken when the dose is lowered or discontinued (see protocol Section 8.5).

Blood sampling for Na, K, bicarbonate, creatinine, and eGFR	X		X	Blood sampling for Na, K, bicarbonate, creatinine, and eGFR will be done at H0 (before start of infusion), H4 (just before furosemide bolus), H5, H6, H7, H8 (or end of infusion ^a) in each treatment period.
Urine sampling for furosemide and BMS-986231 (or its metabolites)	X		X	Urine samples can be taken from the urine collection intervals done for the urinary output (see Table 8 in Section 8.5.1). An aliquot for both sets of metabolites and a back-up will be required for the analysis.

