4 STUDY DESIGN

4.1 Overall Design

This is a double blinded, randomized, two-way cross-over, placebo-controlled study to evaluate the effects of HNO donor BMS-986231 on 4-hour urine output in stable chronic HFrEF patients after administration of 40 mg of IV furosemide. The study consists of 2 one-day treatment periods (BMS-986231 or placebo) separated by a washout period of at least 7 days (Day 2 to at least Day 8), but no more than 4 weeks. Each period includes 8-hour infusion. A standard dose of 40 mg IV furosemide will be administered by IV bolus injection at the midpoint (4 hour, H4) of an 8-hour infusion. Screening for inclusion in the study will be performed up to 4 weeks before the first treatment day (Day 1 of the first period). Approximately 20 eligible subjects will be randomized. For each period, subjects must remain for at least 3.5 hours after the end of infusion. Patients may stay overnight or may be discharged the same day 3.5 hours after end of infusion if certain conditions are met (see Section 4.1). The total duration of the study will be approximately 8 weeks.

Study Drug

BMS-986231 or placebo will be administered in a blinded manner for 8 hours as continuous IV infusion. BMS-986231 will be administered at the dose of 12 μ g/kg/min, corresponding to an infusion rate of 20 mL/H. Placebo will be an infusion of D5W that will be administered at the flow rate of 20 mL/H.

At hour 4 after the start of the infusion, 40 mg IV bolus of furosemide will be administered through a separate IV line, given slowly over 1 to 2 minutes.

In case of significant decrease in SBP at any time during the infusion, an algorithm will be used to down-titrate / interrupt or discontinue the study drug infusion (see Section 6.4 in the protocol).

Screening

Screening for inclusion in the study will be performed up to 4 weeks before the first treatment day. Screening will assess the eligibility criteria. After screening, study participants will be enrolled in the study according to their eligibility as per the inclusion and exclusion criteria, and will be randomized to 1 of the 2 sequences that will be conducted in parallel.

Treatment Day (Day 1 of Each Period)

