4.3 End of Study Definition

The start of the trial is defined as the first visit for the first participant screened. End of trial is defined as the last visit or scheduled procedure shown in [Section 1.3](#), the Schedule of Activities, for the last participant. Study completion is defined as the final date on which data for the primary endpoint was or is expected to be collected.

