16.2.1 Adverse Events

An AE is defined as any new untoward medical occurrence or worsening of a preexisting medical condition in a clinical investigation participant that does not necessarily have a causal relationship with treatment. Treatment-emergent adverse events (TEAEs) are those which occur after the first dose of study drug. All TEAE summaries will be presented alphabetically by system organ class, with preferred terms sorted in decreasing order of frequency within each system organ class based on MedDRA dictionary.

For treatment period assignment, the following rules will be applied:

- TEAEs occurring following dosing in period 1 but before dosing in period 2 will be attributed to the drug administered in period 1.
- TEAEs occurring following dosing in period 2 will be attributed to the drug administered in period 2.

If the time is missing for an AE on a dosing day, then the AE will be attributed to the treatment period of the treatment given on that day.

The following missing data will be imputed (for calculations only) as defined:

- Missing AE start and / or end times for the calculation of onset and duration will be assumed to be at 00:01 for a start time and 23:59 for end times
- Missing AE severity or relationship will be left as missing
- Missing AE start times for the determination of treatment emergence will be assumed to occur after treatment unless partial date documents the AE as happening prior to treatment
- Missing AE start times for the determination of treatment assignment will be assumed to occur after treatment on the recorded date one minute after dosing
- Missing AE start date will be assumed to be after treatment for the determination of TEAE but will not be attributed to a specific treatment

A summary of the number and percentage of subjects reporting AEs, TEAEs by severity, serious AEs (SAEs), and who discontinue study drug due to an AE will be presented by treatment and overall.

A summary of the number and percentage of subjects reporting each TEAE will be presented by treatment and overall. Counting will be done by subject only, not by event; subjects will only be counted once within each body system or preferred term.

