Appendix 2: Schedule of Activities from Protocol

Table 1: Screening Procedural Outline (CV013-034)

Table 2: On Treatment Procedural Outline (CV013-034)

Procedure	Treatment Period			Notes
	Period 1 Day 1	Washout (7-28 days)	Period 2 Day 1	
Washout between periods should be at least 7 days and no more than 4 weeks.				
Safety Assessments				
Weight	X		X	Weight within 15 minutes prior to and within 15 minutes after the end of the infusion in each treatment period with bio-impedance scale. Weight should be measured after the void.
Targeted physical examination	X		X	To be done at H0 (before start of infusion). Based on subject's report since the last visit. Includes temperature, signs and symptoms of congestion. If the screening physical examination is performed within 3 days prior to first dosing then a single physical exam may count as both the screening and at H0 (before start of infusion) evaluation.
Vital Signs (Blood pressure and heart rate)	X		X	Prior to infusion, and 30 minutes for first hour then every 1 hour until discontinuation of infusion, then at H9, H10 and H11.5 (3.5 hour after end of infusion) in each treatment period.
Peripheral Oxygen Saturation	X		X	Prior to the start of infusion and immediately prior to the end of the infusion in each treatment period, measured with a pulse oximeter device.
12-lead ECG	X		X	Prior to the infusion and after end of infusion (both with 15 minutes window) in each treatment period. Triplicate ECGs will be recorded.
Telemetry	X		X	From start of infusion to 3 hours after end of infusion in each treatment period.
Adverse Events Assessment	X		X	Nonserious AEs will be collected from the start of the study drug infusion until 24 hours after end of infusion in each treatment period of dosing. Serious adverse events must be collected from the date of Informed consent and will be assessed up to 30 days after end of infusion of the last period.
			■	
			■	
Follow-up call/assessment	X		X	To be done at Day 2 of each period. Will inquire about general status and occurrence of any AEs.

Table 2:
On Treatment Procedural Outline (CV013-034)

Procedure	Treatment Period		Notes
	Period 1 Day 1	Washout (7-28 days)	Period 2 Day 1
Laboratory Tests			Washout between periods should be at least 7 days and no more than 4 weeks.

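### SAEs are to be collected to 30 days after the last infusion, but the last legible scheduled contact is the Day 2 call of Period 2

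*Protocol*

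**What the plan says.** **The SAE window.** Protocol Section 8.2.1 makes SAE collection mandatory from signed consent and "within 30 days of discontinuation of dosing". In the Schedule of Activities reproduced in SAP Appendix 2, the adverse event row says that SAEs "will be assessed up to 30 days after end of infusion of the last period".

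**The contacts.** Protocol Table 2 (Section 1.3) describes the follow-up call or assessment as "To be done at Day 2 of each period. Will inquire about general status and occurrence of any AEs". No later visit, call or record check is legible in either document. Between the periods, "Washout between periods should be at least 7 days and no more than 4 weeks". At the Period 2 visit there is an adverse event assessment and a targeted examination that takes account of what the patient reports since the last visit (SAP Appendix 2).

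**Related text.** Section 4.3: "End of trial is defined as the last visit or scheduled procedure shown in" the Schedule of Activities. Section 4.1: "The total duration of the study will be approximately 8 weeks". Section 8.2.1 also says: "Investigators are not obligated to actively seek AEs or SAEs in former study participants". Non-serious AEs are collected to 24 hours after end of infusion in each period.

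**Analysis.** SAP Section 16.2.1: "TEAEs occurring following dosing in period 1 but before dosing in period 2 will be attributed to the drug administered in period 1". Events after Period 2 dosing go to the Period 2 drug, with no end date given.

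**The concern.** The plan states a 30-day duty but, as far as can be read, schedules no step that would fulfil it after Period 2. Section 8.2.2 allows events to be reported spontaneously or elicited by open questions. After the Day 2 call of Period 2 no occasion for eliciting is scheduled, so detection depends on the patient or another hospital telling the site. These are heart failure patients who may be admitted elsewhere. Section 8.2.3 requires known SAEs to be followed to resolution, but that does not find new ones. Section 7.1.1 stresses how important follow-up is without scheduling a contact.

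At stake is how an empty SAE listing for the weeks after Period 2 can be read. It could mean that nothing happened or that nobody asked.

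A smaller gap of the same kind concerns non-serious AEs. Their window runs to 24 hours after end of infusion, but the call is fixed only to Day 2, with no minimum interval. A call made before the 24-hour mark complies with the schedule and leaves the rest of the window unasked.

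**Working it through.** **Inputs.** Screening up to 28 days and stated duration about 8 weeks (Protocol 4.1); washout 7 to 28 days and call on Day 2 (Protocol Table 2); SAE window 30 days (Protocol 8.2.1, SAP Appendix 2); about 20 patients allocated 1:1 to two sequences (Protocol 9.1).

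**1. The plan's own duration.** Longest course = screening + Period 1 day + washout + Period 2 day = 28 + 1 + 28 + 1 = 58 days; 58 / 7 = 8.3 weeks. With the Day 2 call it is 59 days, or 8.4 weeks. This reproduces the stated 8 weeks for a schedule that ends at the Day 2 call.

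**2. Days without a scheduled contact after Period 2.** The infusion is on Day 1 and the call on Day 2.
- Window closing 30 days after the infusion, on Day 31: 31 − 2 = 29 days (29 / 30 = 97%).
- Day 1 counted as the first of the 30 days, window closing on Day 30: 30 − 2 = 28 days (28 / 30 = 93%).

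**3. The same interval after Period 1.** The Period 2 visit falls on Day 1 + 7 + 1 = Day 9 at the earliest and Day 1 + 28 + 1 = Day 30 at the latest. Scheduled ascertainment therefore reaches 8 to 29 days after the Period 1 infusion, against 1 day after Period 2. This holds only for patients who return; anyone who withdraws after Period 1 has the Period 2 gap.

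**4. How the gap falls on treatment.** With 1:1 sequences, 20 / 2 = 10 active and 10 placebo infusions are given in Period 2. The shorter ascertainment applies to both about equally.

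**5. Would a 30-day contact fit the stated duration?**

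| Screening | Washout | Days to 30-day contact | Weeks |
|---|---|---|---|
| 28 | 28 | 58 + 30 = 88 | 12.6 |
| 28 | 7 | 28 + 1 + 7 + 1 + 30 = 67 | 9.6 |
| 17 | 7 | 17 + 1 + 7 + 1 + 30 = 56 | 8.0 |

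A 30-day contact fits within 8 weeks only when both windows are short. At the permitted maximum it exceeds 8 weeks by 88 − 56 = 32 days.

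**The case against.** **Redaction.** SAP Appendix 2 has two blacked-out rows directly between the adverse event row and the follow-up call row, and Protocol Table 2 has others. The table has no column after Period 2 Day 1, but that does not settle the matter, because the Day 2 call is itself entered under the Day 1 columns. A hidden row could hold a later contact. This objection stands as a condition on the point.

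**The treatment comparison.** A reader might infer that the adverse event tables by treatment are biased, because Period 2 is watched for less time. The documents do not support that as the main consequence. The non-serious window is 24 hours in both periods, so the difference between periods concerns SAEs, and 1:1 sequences spread it over both treatments. Some imbalance could arise only if dropout differed by sequence.

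**Former participants.** A reader might take the sentence on former participants as releasing sites from asking after Day 2. Nothing says that a patient inside the 30-day window is a former participant, and the same section makes collection mandatory. The status is undefined; it is not a stated exemption.

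**End of trial and lock.** A reader might conclude that the trial ends at the Day 2 call, or that the 8 weeks exclude a later contact. The 30-day SAE assessment is itself written in the Schedule of Activities, so Section 4.3 can be read as already reaching day 30, and the stated duration conflicts only towards the long end of the windows. On lock, SAP Section 3.0 requires a signed SAP; other lock criteria are not described, so their absence shows little.

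**The Day 2 call.** A call at or after 24 hours already complies. The size of any shortfall would need assumed clock times, which the documents do not give.

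**Importance.** Each period has a single 8-hour infusion. The protocol describes preclinical effects partly resolving within 60 minutes (Section 2) and blood pressure recovering within 1 to 2 hours of stopping (Section 8.3). The primary endpoint is untouched. This limits the weight of the point, but the protocol itself chose 30 days.

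**Conclusion.** The gap is real on the legible text. SAEs must be assessed to 30 days after the last infusion, and about 28 to 29 of those days after Period 2 have no scheduled occasion to elicit them. After Period 1 the patient is asked again 8 to 29 days after the infusion.

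The consequence is under-detection of late SAEs after about 20 Period 2 infusions, roughly half active and half placebo. It is not a demonstrated bias between treatments, and it does not affect the urine output analysis. How many events would be missed cannot be estimated from the documents.

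The conclusion assumes that no blacked-out row provides a later contact and that most patients complete both periods. What makes it worth acting on is the small cost of closing the gap.

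**What to change.** - Add one row to Table 2: a telephone contact about 30 days after the end of the last infusion, asking open-ended questions as Section 8.2.2 requires. If a redacted row already provides this, cite it in Section 8.2.1 instead.
- Align the end of trial (Protocol 4.3) and the stated duration (synopsis, Protocol 4.1, SAP 6.0) with that contact, and lock the database after it.
- State that the Day 2 call is made no earlier than 24 hours after end of infusion, so that it covers the whole non-serious AE window.

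**Cost.** About 20 calls by existing site staff, a short amendment, and a last-patient-out up to about 4 weeks later (Day 2 to Day 31 is 29 days). No extra visit or procedure is needed.
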